#### Visit 2: Follow up

This visit will include collection of the monitor and symptom questionnaire, if applicable (paper only).

#### **Analysis**

Simple descriptive statistics will be used to delineate characteristics of the cohort, and the correlation between each pollutant measured by the indoor monitor and day to day symptoms, as determined by the total score on Bronkotest® or ACT. In addition, daily puffs of inhaled short acting treatment (salbutamol) and (asthma only) PEFR will also be examined for relationship to indoor AQ, using a similar correlation analysis. Other factors relating to indoor AQ within collected demographic and medical history data will also be reported using simple comparative statistics.

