#### Study Summary

**Study Title:** A Mixed Methods Observational Study to Determine the Sources and Impact of Indoor Air

Pollution in Patients with Chronic Respiratory Disease.

Internal ref. no. and short title: RG\_21-096; IndoorAirVG

Study Design: Mixed methods study with 3 parts

Part 1: qualitative research exploring patient perceptions and sources of indoor air pollution/poor indoor air quality.

Part 2: questionnaire study to independent group of patients regarding findings of part 1.

Part 3: observational cohort study, distributing indoor air monitors to patients, and gathering symptom and indoor air quality data over a period of 2 weeks.

Study Participants: Subjects with any pre-existing respiratory disease, as determined by their clinician

Planned Size of recruitment target: Part 1: 20-30 patients, Part 2: ≥100 patients, Part 3: 60 patients. There may be overlap between parts 1 or 2 and 3, such that a patient may participate in any one or all three parts of the study.

Follow up duration: Parts 1 and 2: nil. Part 3: 2 weeks

Planned Study Period: 1 year

Research Question/Aim(s): To Determine the Sources and Impact of Indoor Air Pollution in Patients with

Respiratory Disease.

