#### 3. Research question/aims

The study objectives are:

- 1. To identify the environments and/or locations that VGs considered to be important in their exposure to poor air quality indoors. This will be achieved by a combination of qualitative research and questionnaires
- 2. To identify symptom-based health outcomes driven by air quality based on symptoms and indoor air quality monitoring. This will be achieved using a daily symptom diary and an air quality monitor, used over a period of minimum 2 weeks, maximum 6 weeks.

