#### Visit 1: Screening and issue of monitoring device(s)

The informed consent form is signed at this baseline visit. All available information will be collected according to a structured case record form (CRF). Baseline data will be collected including Date of Birth, Sex, Race and ethnicity, Height, Weight, Respiratory Diagnosis, Date of Diagnosis, Severity of disease (clinician defined), Exacerbations in last 12 months, Hospital admissions due to respiratory disease in last 12 months, smoking history, including years as a smoker, year of start and quitting and pack years, working status including relevant occupational exposures and type of agent. Current medication will also be recorded. Consent will be taken to extract from the medical record the latest values for lung function and any relevant radiological results. A symptom questionnaire will be distributed to collect data, and patients with asthma will also receive a peak expiratory flow monitor (if they do not already have one) for conducting daily peak expiratory flow rate (PEFR).

The questionnaire will be delivered in an electronic format compatible with all major phone operating systems, and will utilize validated questionnaires, namely the Bronkotest® questionnaire for patients with COPD and the asthma control test (ACT) for patients with asthma. Those with asthma will also enter their PEFR. Importantly the Bronkotest® system has already been developed for use in an e-diary for another study running locally (a clinical trial, Colour-COPD, funded by NIHR). Adaptation to use ACT is required, but not challenging, and is included in the budget. The Bronkotest® questionnaire will take approximately two minutes to complete each day, while the ACT questionnaire will take around one minute to complete. Self-reported symptoms will be gathered every day over a minimum 2-week period, but if the data in parts 1 and 2 suggests it is required an extension to a period of up to 6-weeks will be considered. If this is required the PIS will be amended with the new timeframe and approval sought for this from ethics. E-diary collection has been shown to result in more complete data than paper forms and be less expensive overall as a result, thus is commonly used in modern respiratory trials. A paper version of the e-diary will be made available for those without a suitable device on which to collect data electronically.

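### The Part 3 analysis is an unadjusted correlation, not defined as within or between patients, so it cannot identify outcomes driven by air quality

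*Protocol*

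**What the plan says.** The Analysis paragraph of Part 3 (Protocol section 4) states the method: "Simple descriptive statistics will be used to delineate characteristics of the cohort, and the correlation between each pollutant measured by the indoor monitor" and day-to-day symptoms, measured by the total Bronkotest or ACT score. Salbutamol puffs and, in asthma, PEFR are to be examined "using a similar correlation analysis". No covariate, stratification or model is named for these estimates. The history data have a separate use: "Other factors relating to indoor AQ within collected demographic and medical history data will also be reported using simple comparative statistics".

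The Visit 1 section lists what is collected at baseline. This includes clinician-defined severity, date of birth, sex and "smoking history, including years as a smoker, year of start and quitting and pack years". Symptoms are then recorded daily for at least two weeks. Calendar date is not a listed variable, but daily diary and monitor records imply it.

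Objective 2 (section 3) is "To identify symptom-based health outcomes driven by air quality based on symptoms and indoor air quality monitoring". The Rationale says that the monitoring study will test whether indoor air can influence daily symptoms. The Background promises only to explore association. The opening of Part 3 calls the study exploratory, and the Recruitment target section says its data will help to power later interventional studies.

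**The concern.** The protocol states its method here, and that method is narrower than the objective it serves. Smoking can raise indoor particulates and worsen symptoms directly. Severity can be related both to time spent indoors and to symptoms. Part 3 sets no limit on severity and smokers are not excluded, so both may vary widely between participants. Either could produce a correlation between pollutant and symptoms without the pollutant acting on symptoms.

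The method is also undefined on a point that decides which biases apply. With at least 14 daily records per patient, the correlation could be taken across patient means, across all pooled person-days, or within patients. Each answers a different question.

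The choice of health outcomes for later intervention studies, and the power calculations for them, are both at stake. A biased correlation would carry into each.

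**Working it through.** **Plan's own figure.** The protocol gives no expected correlation. Its only figure is 30 patients per condition, taken from a two-arm comparison (4% difference in PEFR variability, 80% power, alpha 0.05). The SD is not given, so the figure cannot be reproduced. It would imply an SD of about 5.5 points two-sided. It concerns a difference between arms and does not bear on confounding of a correlation.

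**Spurious correlation from one confounder, no true pollutant effect.** All confounder strengths below are assumptions.

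- *Smoking (binary, prevalence p, effect a SD on the pollutant and b SD on symptoms):* r = p(1−p)ab / √[(1+p(1−p)a²)(1+p(1−p)b²)].
  - p = 0.2, a = 1, b = 0.5: 0.08 / √(1.16 × 1.04) = 0.07.
  - p = 0.3, a = 1.5, b = 1: 0.315 / √(1.4725 × 1.21) = 0.24.
- *Shared seasonal cycle (amplitudes A and B in SD):* r = (AB/2) / √[(1+A²/2)(1+B²/2)].
  - 0.5 and 0.5: 0.125 / 1.125 = 0.11.
  - 1 and 1: 0.5 / 1.5 = 0.33.

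For scale, the two-sided 5% critical |r| at n = 30 is 2.048 / √(28 + 2.048²) = 0.361. Every value above lies below it.

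**How the answer depends on the unit of analysis.** This was simulated with zero true effect, 30 patients × 14 days and 2,000 runs per scenario. Half of the variance in pollutant and symptoms was between patients. One patient-level confounder correlated equally with both. The table gives the share of runs with p < 0.05.

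| Confounder correlation with each | Pooled person-days | Patient means, unadjusted | Patient means, adjusted | Within patient |
|---|---|---|---|---|
| 0 | 32.8% | 4.8% | 4.8% | 5.4% |
| 0.3 | 38.6% | 7.4% | 4.8% | 4.8% |
| 0.5 | 60.2% | 23.2% | 5.0% | 5.0% |
| 0.6 | 78.6% | 45.2% | 5.2% | 4.5% |

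The mean spurious r between patient means was 0.09, 0.22 and 0.33 in the last three rows.

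A shared day-level factor was then added, with loading 0.4 on both series and day-to-day autocorrelation 0.8. The within-patient correlation averaged about 0.10 and crossed p < 0.05 in 51% to 53% of runs.

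Three results follow:

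- Fixed traits such as smoking history and severity bias the between-patient and pooled correlations, and adjustment removes that bias. They do not bias a within-patient correlation.
- A within-patient correlation remains open to anything that moves both series over time.
- Pooling person-days as if independent inflates the error even with no confounding (32.8%), so repeated measures matter at least as much as covariates.

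**Cost of adjustment at patient level.**

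- *Short list:* pollutant, smoking, severity, age and a linear date term, at one parameter each, leave 30 − 5 − 1 = 24 degrees of freedom. The critical partial |r| is 2.064 / √(24 + 2.064²) = 0.39.
- *Long list:* pollutant, smoking, severity, age and sex plus 5 to 11 calendar-month terms make 10 to 16 parameters. That leaves 19 to 13 degrees of freedom, and the critical value rises to about 0.43 to 0.51.

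**The case against.** The strongest reply is that Part 3 is exploratory, places its correlation under descriptive statistics, and states no test, threshold or decision rule. Covariates are also commonly left to an SAP, which is not shown here. This stands in part. The percentages above show susceptibility to bias and are not error rates of a planned test. But the protocol does state a method, and exploratory status does not reconcile that method with a causal objective.

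Several stronger readings are tempting and go too far:

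- *That the plan ignores the history data.* It does not. The last sentence of the Analysis paragraph relates them to indoor air quality. They are missing only from the pollutant–symptom estimate.
- *That confounding would wholly explain, or make significant, any correlation found.* No confounder strength is given in the protocol. The single-confounder values all fall below 0.361, and at 0.3 the inflation between patient means is small (7.4% against 4.8%).
- *That season runs through a full cycle.* "Planned Study Period: 1 year" covers all three parts, and Part 3 draws on Parts 1 and 2. Its own window is not stated, so the seasonal figures are illustrative only.
- *That smoking should simply be adjusted away.* Smoking may itself be a source of the indoor pollution under study, so adjusting for it may remove part of the exposure of interest.

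**Conclusion.** The point holds in a limited form. As written, the analysis yields an unadjusted correlation of unspecified level, which can describe association but cannot meet an objective "To identify symptom-based health outcomes driven by air quality". This rests on the protocol's wording alone. The size of the bias is unknown: the range of about 0.07 to 0.33 depends entirely on assumed confounder strengths, and the simulation on assumed variance shares. An unseen SAP could add adjustment, but it would then be changing the method stated in the protocol, and the wording of Objective 2 would still need attention. The point is worth correcting because the main remedy uses data already planned and Part 3 is meant to inform later trials.

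**What to change.** In the Analysis paragraph of Part 3:

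1. Keep the unadjusted correlation as description, and state whether it is within or between patients.
2. Add beside it, separately for asthma and COPD, a mixed model of each outcome with a patient random effect. Enter exposure as two terms: the patient's mean and the daily deviation from that mean.
3. Adjust for a short list of collected covariates: smoking, clinician-defined severity, and age if numbers allow. Add a linear or smooth date term taken from the diary or monitor dates. Avoid calendar-month categories, which use too many parameters for 30 patients per condition.
4. Show results with and without smoking, since it may be both a confounder and a source.

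In section 3, reword Objective 2 to speak of outcomes associated with air quality, in line with the Background. This is needed even with the model, because a date term removes smooth trends but not day-to-day factors such as infection or weather.

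The cost is a change of wording, a little more analysis and somewhat wider intervals. A daily infection item and linkage to outdoor monitoring would help with day-to-day factors. They need data not now listed and probably an amendment, so they are optional.

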#### 2. Rationale

We have systematically reviewed published work on indoor air quality and its health effects, and found an evidence gap relating to respiratory patients. As such a focus onto this group is required.

Indoor Air Quality VG is a mixed methods study recruiting respiratory patients from within the NHS, and collecting research data remotely/virtually (parts 1 and 2) or in person (part 3). Patients will be managed for their respiratory disease according to their local procedures and policies with no interference from the study team. Patients will give informed consent to participate to each part of the study independently, and will be able to participate in either part 1, 2, and part 3, or one part alone. The key outputs are expected to be (i) A prioritised list of areas in which indoor air quality or indoor/outdoor interfaces (IOIs) contribute to perceptions of respiratory and general health (ii) A list of health outcomes which would be most important to assess in studies of psychological and/or technological interventions identified by other groups working within the parent grant. We anticipate challenges related to the diversity of patients' lives and environments, their understanding of what is possible in short-medium term interventional studies, such as those which may stem from our initial work, and the potential for off target deleterious effects - for example avoiding poor air quality could result in lower physical activity if patients stay in one area, and this is known to be harmful to health[10, 11]. For this reason, we have chosen a mixed method design where we can fully explore views in an initial qualitative package, before refining our inquiry in a questionnaire to a larger group of patients, independent of those participating in the qualitative work. We will then test the potential for indoor air to influence day to day symptoms by way of a short-term monitoring study.

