#### Part 3: Quantifying indoor AQ and respiratory symptoms

This part of the study will recruit approximately 60 patients, aiming for an equal distribution of people with asthma and people with COPD. Any severity stage will be allowed. In a study of an air purifier in asthmatic children a 4% difference in PEFR variability was seen [5]; the study had power 80% and  $\alpha$ =0.05, and it was possible to detect this with 30 patients in each arm of a study. Consequently, we feel that 30 is a reasonable target per condition in an exploratory study of this nature in adults.

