#### **Recruitment target**

#### Size of recruitment target

The target sample size is based on experiences with similar projects, with 30 likely to be sufficient to reach data saturation, and 100 likely to give sufficient pilot data to design onward studies of interventions (parts 1 and 2 respectively). The number of patients who can have home monitoring is a pragmatic choice made from availability of monitors and knowledge of sample size in other interventional studies; without data on the extent to which indoor AQ relates to symptoms in COPD and asthma it is impossible to conduct a robust power calculation. Notably the data from part 3 of the study would be used to aid power calculations for onward interventional studies.

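### Part 3 plans a correlation of pollutants with daily scores without a within-patient step, so it does not isolate the day-to-day association the study sets out to examine

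*Protocol*

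**What the plan says.** The Analysis section of Part 3 opens with "Simple descriptive statistics will be used to delineate characteristics of the cohort" and, in the same sentence, adds "the correlation between each pollutant measured by the indoor monitor and day to day symptoms", symptoms being the total Bronkotest or ACT score. Salbutamol puffs and, in asthma, PEFR are to be related to indoor air "using a similar correlation analysis". The section names no unit of analysis, no patient term and no method for repeated measures.

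The data are daily. Under Visit 1, "Self-reported symptoms will be gathered every day over a minimum 2-week period", and "an extension to a period of up to 6-weeks will be considered". On size, "This part of the study will recruit approximately 60 patients", split about equally between asthma and COPD, so roughly 30 per condition.

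On purpose, the Rationale states: "We will then test the potential for indoor air to influence day to day symptoms by way of a short-term monitoring study". The section on size of recruitment target adds that "the data from part 3 of the study would be used to aid power calculations for onward interventional studies".

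**The concern.** Whether indoor air influences symptoms from one day to the next is most naturally a question about change within a patient: on days when this person's exposure is above their own usual level, are their symptoms worse? Patients also differ persistently from one another, in their homes, smoking, disease severity and, for raw PEFR, body size. Part 3 admits any severity stage, and eligibility is deliberately broad, so these stable differences are likely to be large.

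A correlation that ignores which patient a row came from mixes the two sources. It can be clearly positive when nothing happens from day to day, or close to zero, or of the wrong sign, when a daily association exists. A correlation of patient means avoids the mixing but answers only the between-patient question. The reported coefficient could therefore mislead readers about objective 2 and those who design the onward interventional studies.

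**Working it through.** **The plan's own figure.** The protocol gives no calculation for the correlation. Its 30 per condition is borrowed from a cited two-arm study (4% difference in PEFR variability, 80% power, alpha 0.05). The SD is not given, so the figure cannot be confirmed. With two-sided alpha it needs an SD of about 5.5 percentage points (n = 30 per arm, power 0.804). It concerns a difference in means and does not bear on the correlation beyond setting the number of patients.

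**Inputs.** From the protocol: n = 30 patients per condition; d = 14 days (minimum) or 42 days (6 weeks). Assumed, because the protocol gives none: intraclass correlations (ICCs) for pollutant and score of 0.5 and 0.7, with a range from 0.3/0.5 to 0.7/0.8.

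**1. What a pooled coefficient estimates.** With between-patient correlation rB and within-patient correlation rW,

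pooled r ≈ rB × √(ICCx × ICCy) + rW × √((1 − ICCx)(1 − ICCy)).

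| Truth | ICCs 0.3/0.5 | ICCs 0.5/0.7 | ICCs 0.7/0.8 |
|---|---|---|---|
| rB = 0.4, rW = 0 | 0.4 × √0.15 = 0.15 | 0.4 × √0.35 = 0.24 | 0.4 × √0.56 = 0.30 |
| rB = 0, rW = 0.2 | 0.2 × √0.35 = 0.12 | 0.2 × √0.15 = 0.08 | 0.2 × √0.06 = 0.05 |

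The first row has no daily association, yet it gives the larger coefficient throughout. If rB = −0.3 and rW = 0.2, ICCs of 0.5/0.7 give −0.18 + 0.08 = −0.10, the wrong sign for the daily question. Simulation with both ICCs at 0.6 (30 × 14, 2,000 runs) agreed: 0.24, 0.08 and −0.09 for the three cases. The patient-centred correlation gave 0.00, 0.20 and 0.20.

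**2. What a correlation of patient means estimates.** In the same simulation, with rW = 0.2 and rB = 0, a 5% test on patient means rejected in 4.5% of runs, which is no better than chance. The patient-centred analysis rejected in 98%. With independent days and no association, the test on means kept its level (about 4% to 6%). It is valid, but for a different question.

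**3. If a test or interval were attached to the pooled coefficient.** Design effect DE = 1 + (d − 1) × ICCx × ICCy; actual error of a nominal 5% test ≈ 2 × (1 − Φ(1.96/√DE)). For d = 14 there are 30 × 14 = 420 rows:

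| ICCs | DE | Effective rows | Actual error |
|---|---|---|---|
| 0.3/0.5 | 1 + 13 × 0.15 = 2.95 | 142 | 25% |
| 0.5/0.7 | 1 + 13 × 0.35 = 5.55 | 76 | 40% |
| 0.7/0.8 | 1 + 13 × 0.56 = 8.28 | 51 | 50% |

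Simulation gave 26% and 40% for the first two rows. At 42 days it gave 47% and 64%, so a longer diary makes this worse. The patient-centred correlation stayed at about 3% to 6% in all settings. With autocorrelation of 0.3 between days added, patient-clustered standard errors kept it at about 5% to 6%, with about 95% power at rW = 0.2.

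**The case against.** The strongest reply is that the protocol does not say patient-days are pooled. It names no coefficient and no unit of analysis. The word simple is attached to descriptive and comparative statistics, not to the correlation. A repeated-measures correlation is still a correlation, so the wording does not forbid it, and the choice could be left to an analysis plan. This stands in part: pooling is a likely reading, not a stated one. But the section is not silent. It settles on a correlation within simple descriptive statistics, and neither ordinary way of computing it isolates the daily association. That makes it a method poorly fixed, not a detail left open.

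A reader might infer that Part 3 will produce false-positive findings at 40% or so. The documents do not support that. The Analysis section plans no p-value, interval or alpha, the 0.05 in Part 3 belongs to the cited study, and the work is called exploratory. Only the verb in the Rationale hints at a test. The error rates in step 3 depend on both pooling and testing. The blending in step 1 depends on pooling alone.

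A reader might also infer that the onward power calculations are compromised. The protocol relies there on the Part 3 data, not on the coefficient, and slopes and SDs can be computed from the daily records at any time.

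Finally, the Background introduces day-to-day symptoms as a type of outcome, in contrast with admissions and long-term decline in lung function, so the within-patient reading is not explicit. It remains the natural one for a daily diary paired with a monitor and for the wording of the Rationale.

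**Conclusion.** The point holds in this form: as worded, the Part 3 analysis does not isolate the day-to-day association. If patient-days are pooled, the coefficient blends two associations: about 0.24 with no daily effect when the between-patient correlation is 0.4, and about 0.08 when the only association is a within-patient 0.2. If patient means are used, the daily signal is lost. Any p-value or interval on the pooled coefficient would be too optimistic, with a type I error of about 25% to 50% at 14 days, but none is planned.

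All sizes rest on assumed ICCs and assumed correlations. The error inflation becomes small only if the ICC of pollutant or score is near zero, which is unlikely across different homes and severity stages. A reader might see this as a flaw that invalidates Part 3. It is not: the study is exploratory and the daily data can be fully re-analysed. It should be fixed before analysis.

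**What to change.** In the Part 3 Analysis section, replace the plain correlation, separately for asthma and COPD, with a within-patient analysis. Two options serve:

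- a repeated-measures correlation; or
- a mixed model with a random patient intercept, with the patient's mean pollutant level and the daily deviation from it as separate terms. The two terms are needed, because a random intercept with a single pollutant term would still mix the two associations.

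Make the daily-deviation association the main result, with standard errors that allow for clustering and serial correlation within patient. Report the slope and the within- and between-patient SDs for the onward power calculations. Apply the same approach to salbutamol puffs and PEFR. Choices such as a log scale for the pollutant, a count model for puffs or covariate adjustment can be left to the analysis plan. An exposure window tied to diary entry would need entry times, which the protocol does not say are collected.

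Cost: a few sentences of text, slightly more analyst time, and a protocol amendment through the sponsor and ethics route already described. No new data and no extra patients.
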